## 8.6 Follow-up of subjects withdrawn from treatment

N.A.

## 8.7 Premature termination of the study

It is not expected that adverse events will happen that will result in premature termination of the study. Though the study might be terminated prematurely when:

- An agency's (for example METC) approval is withdrawn
- The department withdraws the study
- If inclusion of patients is disturbed due to unforeseen circumstances

## 9. SAFETY REPORTING

### 9.1 Temporary halt for reasons of subject safety

In accordance to section 10, subsection 4, of the WMO, the sponsor will suspend the study if there is sufficient ground that continuation of the study will jeopardise subject health or safety. The sponsor will notify the accredited METC without undue delay of a temporary halt including the reason for such an action. The study will be suspended pending a further positive decision by the accredited METC. The investigator will take care that all subjects are kept informed.

### 9.2 AEs, SAEs and SUSARs

#### 9.2.1 Adverse events (AEs)

Adverse events are defined as any undesirable experience occurring to a subject during the study, whether or not considered related to the investigational product / trial procedure/ the experimental intervention. All adverse events reported spontaneously by the subject or observed by the investigator or his staff will be recorded. However, as no medication will be used, and no further invasive measurements are performed, we expect no adverse events from the device. Potential adverse events that might occur during treadmill exercise are: Dyspnea, falling accidents, and exhaustion.

#### 9.2.2 Serious adverse events (SAEs)

A serious adverse event is any untoward medical occurrence or effect that

- results in death;
- is life threatening (at the time of the event);
- requires hospitalisation or prolongation of existing inpatients' hospitalisation;
- results in persistent or significant disability or incapacity;
- is a congenital anomaly or birth defect; or
- any other important medical event that did not result in any of the outcomes listed above due to medical or surgical intervention but could have been based upon appropriate judgement by the investigator.

An elective hospital admission will not be considered as a serious adverse event.

The investigator will report all SAEs to the sponsor without undue delay after obtaining knowledge of the events, except for the following SAEs: Non excluded.

The sponsor will report the SAEs through the web portal *ToetsingOnline* to the accredited METC that approved the protocol, within seven days of first knowledge for SAEs that result in

death or are life threatening followed by a period of maximum of eight days to complete the initial preliminary report. All other SAEs will be reported within a period of maximum fifteen days after the sponsor has first knowledge of the serious adverse events.

### **9.2.3 Suspected unexpected serious adverse reactions (SUSARs)**

N.A.

### **9.3 Annual safety report**

N.A.

### **9.4 Follow-up of adverse events**

All AEs will be followed until they have abated, or until a stable situation has been reached. Depending on the event, follow up may require additional tests or medical procedures as indicated, and/or referral to the general physician or a medical specialist.

SAEs need to be reported till end of study within the Netherlands, as defined in the protocol

### **9.5 Data Safety Monitoring Board (DSMB) / Safety Committee**

N.A.

## 10. STATISTICAL ANALYSIS

Intra-class correlation coefficients will be calculated as indicated below and described using 95% confidence intervals.

### 10.1 Primary study parameter(s)

The primary endpoint of inter-observer variability will be the intraclass correlation coefficient (ICC) of agreement between three observers, four sites per subject, and four repetitions per measurement. The ICC will be assessed using a two-way random effects model. Both observers and subjects will be included as random effects. The first measurement for each location will be taken from every observer to calculate the ICC. Apart from that, the ICC will be measured using the average of the four repetitions of ratings, to estimate the effect on the ICC of repetitive measurements. “Good reliability” classification will be reached if the lower bound of the computed ICC confidence interval does not fall below 0.75.

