### 3. STUDY DESIGN

A performance validation pilot of the CPM#1 device in healthy volunteers. There will only be one study arm, no comparator, and no randomization. Participants participate in one 60-minute study visit (one session) and no follow-up is planned. The total study duration is three months.

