#### 4.4 Sample size calculation

As data on this device are scarce, a pragmatic sample size rationale is pursued based on previous studies that were made available to us by the company. Moreover, this study is not aimed at hypothesis testing, rather, we aim to estimate the ICC with certain precision. With the predecessor of CPM#1 it has been shown that an  $ICC \geq 0.75$  is achievable and thus demonstrated a good inter-observer reliability.

[figure not shown]
Measuring the left and right m. tibialis anterior in two directions, an expected  $ICC = 0.8$  (based on bench tests) and a one-sided 95% target confidence interval width of 0.05 based on three observers, a sample size of 140 is required. Since we measure 4 'samples' per participant (each leg the m.tibialis anterior at two different approaches, see section 5.1), we aim to include 35 healthy volunteers (140:4). We do not include dropouts in our calculation since we perform only one 90 minute session without follow-up. Participants who do not complete the

measurements will be replaced for new inclusions, such that we will have a complete data set of 35 participants in the end.

To power for the measurement directly after exercise, using dependent sample T-test with an expected effect size of 0.4 (based on results from bench test), an  $\alpha$  of 0.05 and power ( $\beta-1$ ) of 0.9, we would require 68 samples. Since the strict timing of the measurements after exercise only allows the measurement of one sample (one compartment using one approach), all participants will undergo two exercise sessions ( $2 \times 35 = 70$ ).

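### The 0.05 precision behind 35 volunteers is a two-sided half-width that assumes independent sites and no observer variance; restate it, and compute the interval for the 0.75 rule to fit the design

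*Combined protocol and SAP*

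**What the plan says.** Section 4.4 sets the sample size on precision: "this study is not aimed at hypothesis testing, rather, we aim to estimate the ICC with certain precision". With an expected ICC of 0.8 it asks for "a one-sided 95% target confidence interval width of 0.05 based on three observers, a sample size of 140 is required", and divides 140 by four sites per participant (two legs, two landmarks) to reach 35 people. Section 3 describes the study as "A performance validation pilot of the CPM#1 device in healthy volunteers".

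Section 8.1.1 defines the endpoint as a two-way random-effects, single-observer, absolute-agreement ICC. Section 10.1 confirms the model: "Both observers and subjects will be included as random effects". It describes two ICCs. For the first, "The first measurement for each location will be taken from every observer to calculate the ICC". The second follows with "Apart from that, the ICC will be measured using the average of the four repetitions of ratings", in order to see what repetition does to the ICC. The label is then given "if the lower bound of the computed ICC confidence interval does not fall below 0.75". Section 10.2 repeats this rule for the intra-observer ICC. Section 10 promises 95% confidence intervals without stating sidedness. Neither 10.1 nor 10.2 says how the interval treats four sites from one person.

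**The concern.** The 0.05 is the whole basis for 35 people, and three things about it need attention.

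- **Label.** Read literally, a one-sided 95% bound at distance 0.05 is a different target from the one that yields 140.
- **Assumptions.** The calculation has no term for systematic differences between observers and treats each site as a separate unit. Absolute agreement counts observer differences as error, and with only three observers their variance is poorly estimated. Four sites on one person are likely to resemble each other.
- **Position.** The expected ICC minus the target width equals the cut-off, so small changes in precision or in the choice of bound move the label.

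At stake are an overstated precision and, if the analysis treats the 140 sites as independent, an interval that is too narrow deciding the label.

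**Working it through.** **Inputs.** ICC ρ = 0.80, k = 3 observers, 95%, 0.05, 140 samples, 35 × 4 (section 4.4); cut-off 0.75 (section 10.1); ICC form (section 8.1.1). The visible text names no formula. I used Bonett's precision formula for an ICC, with w the full interval width:

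n = 1 + 8 z² (1 - ρ)² [1 + (k - 1)ρ]² / [k(k - 1) w²]

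**Step 1: reproduce 140.** (0.2)² × (2.6)² = 0.04 × 6.76 = 0.2704, and 8 × 0.2704 = 2.1632. For w = 0.10 the divisor is 6 × 0.01 = 0.06, giving 36.05. For w = 0.05 it is 6 × 0.0025 = 0.015, giving 144.21.

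| Reading of the 0.05 | z | n |
|---|---|---|
| Two-sided, half-width 0.05 | 1.960 | 1 + 3.8415 × 36.05 = 139.5, so 140 |
| One-sided bound, distance 0.05 | 1.645 | 1 + 2.7055 × 36.05 = 98.5, so 99 |
| Two-sided, full width 0.05 | 1.960 | 555 |
| z = 1.645, full width 0.05 | 1.645 | 392 |

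Only the first row gives the plan's figure.

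**Step 2: position against the cut-off.** 0.80 - 0.05 = 0.75. With F-based limits at an observed ICC of 0.80 and n = 140, the two-sided 95% interval is 0.746 to 0.846 and the one-sided 95% lower bound is 0.755. At the planning value the first misses the cut-off and the second meets it.

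**Step 3: chance of the label on the plan's own assumptions.** With independent sites and no observer variance, the lower limit reaches 0.75 when the between/within mean-square ratio is at least F(0.975; 139, 280) × (1 + 2 × 0.75)/(1 - 0.75) = 10 × F(0.975; 139, 280). At a true ICC of 0.80 that ratio is distributed as 2.6/0.2 = 13 times an F variable. The probability is 44%. It is 18% at 0.78 and 98% at 0.85.

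**Step 4: precision for the stated design.** Simulated absolute-agreement ICC, true value 0.80, 35 people × 4 sites × 3 observers, first measurement only. Entries are 1.96 × SD of the estimate. The documents give no variance shares, so every row and column is an assumption.

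| Site variance shared within a person | Observer share 0 | 2% | 5% |
|---|---|---|---|
| 0 | 0.051 | 0.058 | 0.087 |
| 25% | 0.053 | 0.061 | 0.089 |
| 50% | 0.061 | 0.068 | 0.094 |
| 75% | 0.073 | 0.078 | 0.102 |

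The top-left cell is the plan's case (0.0499 by formula). Repeat runs differ by about 0.001; the 75% entry with no observer variance came out between 0.072 and 0.074.

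**Step 5: what an unclustered interval shows.** With no observer variance, an interval that treats the 140 sites as independent still displays a half-width of about 0.051. Its coverage falls to about 90% at 50% shared variance and 84% at 75%.

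**Step 6: which ICC.** If 25% to 100% of the 0.20 error variance is repetition error (assumed), averaging four repetitions raises an ICC of 0.80 to between 0.83 and 0.94. For example, 0.8/(0.8 + 0.20/4) = 0.94. The two ICCs in 10.1 can therefore give different labels.

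**The case against.** **The wording in 4.4 can be read innocently.** One-sided width may simply mean the width on one side of the estimate, which gives 140. A figure in 4.4 is not shown and may define the term. This stands: a reader might infer that 140 is wrong or that 4.4 contradicts section 10, but under the half-width reading the sections agree.

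**This is a precision-based pilot.** A reader might infer from the 44% that the study is underpowered and needs more people. The documents do not support that. Section 4.4 disclaims hypothesis testing, no consequence is attached to missing the label, and the ICC and interval are reported either way. Prior values also point both ways: section 1 cites inter-observer reliabilities of 0.78 and, from unpublished bench data, 0.945. Stating a pass probability is therefore optional.

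**The deciding ICC is largely settled.** A reader might infer that the sponsor is free to choose between two ICCs. But 10.1 uses the first measurement to calculate the ICC and brings in the mean of four for another purpose. Only a clarification is needed.

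**The variance shares are invented.** True, so the sizes are illustrative. The direction is not: observer variance or positive within-person correlation each makes 0.05 too favourable.

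**Section 10.1 names subjects, not sites, as the random effect.** That could signal an analysis by person, but 4.4 counts 140 separate samples and no section says how the four sites enter. This supports specifying the interval.

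**Conclusion.** The concern holds in a limited form. The 140 is correctly calculated for a two-sided 95% half-width of 0.05, and its label should say so. As a statement of precision for the declared endpoint, 0.05 is too favourable. Plausible values run from 0.053 to 0.102 over the assumed grid of up to 75% within-person sharing and up to 5% observer share; 50% sharing with a 2% or 5% observer share gives 0.068 or 0.094. Because the planned lower limit coincides with 0.75, the interval method matters for the label, and one that ignores clustering would be too narrow. The arithmetic on 140 is firm, given the standard formula. The sizes in steps 4 and 5 depend on assumed variance shares.

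**What to change.** 1. **Section 4.4.** Describe the target as a two-sided 95% confidence interval with half-width 0.05, assuming independent sites and no observer variance. Add the expected precision as a range under plausible observer variance and within-person correlation. Keep 35 participants. Optionally note that, on the plan's assumptions, the label is met about 44% of the time at ICC 0.80.
2. **Sections 10.1 and 10.2.** State that each rule uses the lower limit of a two-sided 95% interval that respects four sites per participant: for example, a person random effect with sites nested within person, or resampling by participant. In 10.1 keep observers random. Resampling participants alone would hold the three observers fixed, so observer variance must still enter the interval.
3. **Section 10.1, minor.** State that the rule uses the first-measurement, single-observer, absolute-agreement ICC, and that the four-repetition-mean ICC is supportive.

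Cost: no new data or participants, a somewhat more complex interval, and a less favourable stated precision. Naming the first-measurement ICC also gives up any gain that averaging four repetitions would bring to the label.

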### 10.2 Secondary study parameter(s)

The secondary endpoint of intra-observer variability will be the intraclass correlation coefficient (ICC) of agreement within three observers, four sites per subject, and four repetitions per measurement. The ICC will be assessed using a two-way random effects model. Both subjects and repetitions will be included as random effects. The repeated measures will be analysed for each observer separately and this agreement serves to address differences between observers. “Good reliability” classification will be reached if the lower bound of the computed ICC confidence interval does not fall below 0.75

The second secondary endpoint is the comparison between post-exercise (immediate, one minute, and five minutes) compressibility and rest compressibility. This will be analysed using a dependent sample t-test.

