### 5.1 Investigational product/treatment

All 35 healthy subjects will undergo four times four measurements in rest (m. tibialis anterior of both legs, using two different internal landmarks). Although the 'tibial notch' between the interosseous membrane and the tibial bone was previously suggested as the optimal landmark, recent data from our department suggest that the middle of the interosseous membrane is less variable. These four times four measurements in rest will each be done by three observers.

To measure the effect of exercise, compressibility will be measured immediately, one minute, and five minutes after a standard treadmill exercise at just one leg. The treadmill exercise and the corresponding measurements will be performed twice to include measurements of both legs. The measurements after exercise will be performed by only one observer.

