#### 8.1.2 Secondary study parameters/endpoints (if applicable)

Intra-observer variance of compressibility within three observers using intra-class correlation coefficients (two-way random effects, single observer, absolute agreement).

Immediate, one minute, and five minutes post-exercise compressibility compared to the observer's rest measurement compressibility.

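### Section 10.2 relies on three separate per-observer ICCs to address differences between observers, but plans no estimate of such a difference and would often miss a moderate one

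*Combined protocol and SAP*

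**What the plan says.** Section 10.2 assesses intra-observer reliability with a two-way random effects ICC. On its terms it says "Both subjects and repetitions will be included as random effects", so the model has no observer term. It continues: "The repeated measures will be analysed for each observer separately and this agreement serves to address differences between observers". Section 10 sets the form of reporting: "Intra-class correlation coefficients will be calculated as indicated below and described using 95% confidence intervals". Each ICC also gets a good-reliability label, "reached if the lower bound of the computed ICC confidence interval does not fall below 0.75".

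The design is fully crossed. Section 5.1 states "These four times four measurements in rest will each be done by three observers", and Section 4.4 counts four sites per participant ("Since we measure 4 'samples' per participant"), giving 35 × 4 = 140 sites.

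Section 10.1 does model observers jointly, but its output is a pooled inter-observer ICC. That ICC reflects offsets between observers and does not show which observer repeats less precisely. Section 10.3 leaves room for further exploratory analyses and names none on this point.

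**The concern.** The quoted sentence gives the per-observer analysis a comparative purpose, but no comparison follows: no joint model, no difference or ratio, and no interval for either.

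A per-observer ICC sets an observer's repeat error against the spread between sites. That spread is largely common to the three observers because they read the same sites. Its sampling error widens each separate interval, yet mostly cancels when observers are compared. What distinguishes observers in precision is their repeat error, which these data estimate well and the plan never compares.

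Two misreadings are possible. Overlapping intervals could be taken to mean equally consistent observers when the data show otherwise. Different 0.75 labels could be taken to mean a difference when there is none. Both matter for a hand-held device whose results may depend on who holds it.

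**Working it through.** **Inputs.** From the plan: 35 participants, 4 sites each, 3 observers, 4 repeats, expected ICC 0.8, label threshold 0.75 (Sections 4.4, 5.1, 10.2), and cited intra-observer ICCs of 0.89 and 0.79 (Section 1). The plan gives no variance components, so the simulations assume them: the share of site variance common to a participant's sites is 0 or 0.5, and the site-by-observer share of between-site variance is 0 to 0.2. The site is taken as the unit of the ICC, as in Section 4.4.

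**The plan's own figure.** Section 4.4 says "one-sided 95% target confidence interval width of 0.05 based on three observers, a sample size of 140 is required". The Bonett formula is n = 8z²(1−r)²(1+(k−1)r)² / (k(k−1)w²) + 1. With z = 1.96, r = 0.8, k = 3 and total width w = 0.10, n = 8 × 3.8415 × 0.04 × 6.76 / (6 × 0.01) + 1 = 139.5, so 140. The figure reproduces as a two-sided 95% interval of half-width 0.05.

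**Why the labels are unstable at the planning value.** A half-width of 0.05 around 0.80 puts the expected lower bound at 0.75, exactly on the threshold. With k = 4 repeats and n = 140, w² = 8 × 3.8415 × 0.04 × 11.56 / (12 × 139) = 0.00852. The half-width is then 0.046 and the lower bound about 0.754. Two observers with the same true ICC of 0.80 therefore received different labels in 22 to 37% of simulated runs.

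**Separate intervals, ICC 0.84 against 0.79.** With F₀ = 1 + k·ICC/(1−ICC), F₀ is 22 for 0.84 and 16.05 for 0.79. The F-based 95% intervals expected with 140 sites and 4 repeats are 0.799 to 0.876 and 0.739 to 0.835. They overlap.

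**Direct comparison, same pair.** Scale the between-site variance to 1, so the repeat variance is (1−ICC)/ICC.
- The ratio is (0.21/0.79)/(0.16/0.84) = 0.2658/0.1905 = 1.40, an SD ratio of 1.18.
- Each variance has 140 × 3 = 420 df, so under normal errors the SE of the log variance ratio is √(2/420 + 2/420) = 0.098.
- The SE of the log SD ratio is 0.049, giving an approximate 95% interval for the SD ratio of 1.07 to 1.30.
- At level 0.05/3 (three observer pairs, critical value 2.39) the signal is 0.333/0.0976 = 3.42. The chance of detection is Φ(3.42 − 2.39), about 85%.

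**Simulation, normal errors (600 to 3,000 runs per scenario).** The direct comparison is of repeat variances on the shared sites, by F-test or participant-level jackknife.

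| True ICCs | Variance ratio | Separate 95% CIs do not overlap | Direct comparison (level) |
|---|---|---|---|
| 0.80 vs 0.75 | 1.33 | 1–3% | 79–82% (0.05) |
| 0.84 vs 0.79 | 1.40 | 2–4% | 81–85% (0.05/3) |
| 0.85 vs 0.80 | 1.42 | 3–9% | 91–94% (0.05) |
| 0.85 vs 0.78 | 1.60 | 18–26% | over 99% (0.05) |
| 0.86 vs 0.79 | 1.63 | 23–28% | over 99% (0.05/3) |
| 0.89 vs 0.79 | 2.15 | 90–96% | 100% (0.05) |

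The reason is visible in the ICC estimates. Across scenarios they correlate at about 0.42 to 0.80 between observers. With both ICCs at 0.80, the SD of their difference is 0.019 to 0.026, against 0.034 to 0.042 if they are treated as independent.

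**Paired ICC difference.** With a participant-level jackknife at the 5% level, this finds 36–60% (0.80 vs 0.75) and 54–82% (0.85 vs 0.80). It lies between the two approaches.

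**Non-normal errors.** With equal observers, t errors on 5 df or a repeat SD that varies between sites (log-SD 0.5, assumed) make the F-test reject in 12 to 14% of runs against a nominal 1.7%. The participant-level jackknife stays at 1 to 2%. Under such errors it detects about 42% (0.84 vs 0.79) and 75% (0.86 vs 0.79) at 0.05/3, while interval non-overlap gives about 8% and 30%.

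**The case against.** **The study estimates; it does not test.** Section 4.4 says so, ranking observers is not among the objectives in Section 2, and a per-observer ICC with its interval validly answers the stated intra-observer question. This stands. It argues against adding a formal test, but does not explain why the comparison that Section 10.2 mentions has no estimate.

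**The comparison rule is assumed.** The plan nowhere says that overlapping intervals will be read as equality. The quoted sentence could also mean only that observers are analysed separately so that their differences do not contaminate repeatability. On that reading the analysis is sound and only the wording needs clarifying.

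**The contrast is not like for like.** Non-overlap of two independent 95% intervals with equal standard errors works at about 0.6%, stricter than 0.05/3, and an ICC is a different quantity from a repeat variance. This is partly right, but strictness is not the main cause. A z-test treating the two ICCs as independent, also at 0.05/3, finds 7% for 0.84 vs 0.79 and 46% for 0.86 vs 0.79, against 85% and over 99% for the repeat variances.

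**No document says an SD ratio near 1.18 matters.** True. The plan sets no relevant size of difference, which is a reason to report the ratio with its interval and leave its importance to the reader.

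**Readings that go too far.** A reader might infer that separate ICCs would miss any difference. They would not: a gap of 0.89 against 0.79 shows in 90 to 96% of runs. A reader might also infer that such a gap is to be expected here. Section 1 reports those values by experience in a cited study of healthy subjects, and the protocol does not say that its three observers differ in experience.

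**Conclusion.** The point holds for moderate differences in precision. Section 10.2 names differences between observers as a purpose and supplies no estimate of them, and no other section does. Reading the separate intervals side by side would often miss ICC gaps of about 0.05 to 0.07 (1 to 9% non-overlap at a gap of 0.05, 18 to 28% at 0.07). A direct comparison on the shared sites finds most of them under normal errors. The 0.75 labels can also separate observers who are equal.

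The figures rest on assumed variance components, the site as unit, and interval overlap or the labels as the reader's only means of comparison. With heavy-tailed or site-varying errors the advantage of a robust method shrinks but remains clear.

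The primary inter-observer ICC, the validity of each per-observer ICC and the sample size are unaffected. This is a low-cost improvement to a secondary analysis.

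**What to change.** Keep the per-observer ICCs and the 0.75 rule as description. In Section 10.2, replace the last clause of the sentence on separate analysis with:

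*Differences in repeatability between observers are described by the within-observer SD of each observer and the pairwise SD ratios (and, if wanted, paired ICC differences) on the shared sites, with 95% CIs from participant-level bootstrap or jackknife.*

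Resampling whole participants respects the four sites within each person and does not depend on normal errors. Do not add a normal-theory F-test or likelihood-ratio test of equal variances: its error rate is inflated under plausible departures from normality, and the study aims at estimation. If no comparison between observers is intended, delete the clause.

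The cost is one sentence and one extra analysis on data already collected, with no added measurements or participants. The price of robustness is lower sensitivity when errors are not normal, as shown in the working.
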